8.2.6 Pregnancy testing

For female participants of childbearing potential, a pregnancy test will be performed at each visit during the whole study period. A serum pregnancy test will be conducted at the Screening Visit, and a urine pregnancy test will be performed for all other visits. For WOCBP, monthly urine pregnancy tests will be provided directly to participants for those not coinciding with a clinic visit. Results should not be older than 24 hours upon intake of first dose of IMP.

8.2.7 Suicidal ideation and behavior risk monitoring

SAR443820 crosses the blood-brain barrier. Assessment of suicidal ideation and behavior/treatment-emergent suicidal ideation and behavior will be monitored during ACT16753 using the C-SSRS. For safety reasons, the C-SSRS will be administered throughout the study by the Investigator or delegated to an individual who is certified to administer the scale.

Study intervention administration must be interrupted if a participant scores “yes” on item 4 or 5 of the Suicidal Ideation Section of the C-SSRS or “yes” on any item of the Suicidal Behavior Section. A mental health professional will be consulted and will decide whether the study intervention can be restarted and if any additional risk mitigation strategies are required (eg, increased monitoring, antidepressant administration).

Participants being treated with the study intervention should be monitored appropriately and observed closely for suicidal ideation and behavior (SIB) or any other unusual changes in behavior, especially at the beginning and end of the course of intervention, or at the time of dose changes, either increases or decreases. Participants who experience signs of SIB, should undergo a risk assessment. All factors contributing to SIB should be evaluated and consideration should be given to discontinuation of the study intervention.

8.3 ADVERSE EVENTS (AES), SERIOUS ADVERSE EVENTS (SAES) AND OTHER SAFETY REPORTING

The definitions of AEs and SAEs can be found in Appendix 3 ([Section 10.3](#)). The definition of AESI is provided in [Section 8.3.9](#).

The definitions of unsolicited and solicited AEs can be found in Appendix 3 ([Section 10.3](#)).

Adverse events will be reported by the participant (or, when appropriate, by a caregiver, surrogate, or the participant’s legally authorized representative).

The Investigator and any qualified designees are responsible for detecting, documenting, and recording events reported by the participant (or, when appropriate, by a caregiver, surrogate, or the participant’s legally authorized representative) that meet the definition of an AE or SAE and remain responsible for following up AEs that are serious, considered related to the study intervention or study procedures, or caused the participant to discontinue the study intervention (see [Section 7](#)).

The method of recording, evaluating, and assessing causality of AEs and SAEs and the procedures for completing and transmitting SAE reports are provided in Appendix 3 ([Section 10.3](#)).

8.3.1 Time period and frequency for collecting AE and SAE information

All AEs (serious or nonserious) will be collected from the signing of the ICF until the follow-up visit at the timepoints specified in the SoA ([Section 1.3](#)).

All SAEs and AESI will be recorded and reported to the Sponsor or designee immediately and under no circumstance should this exceed 24 hours, as indicated in Appendix 3 ([Section 10.3](#)). The Investigator will submit any updated SAE data to the Sponsor within 24 hours of it being available.

Investigators are not obligated to actively seek information on AEs or SAEs after conclusion of the study participation. However, if the Investigator learns of any SAE, including a death, at any time after a participant has been discharged from the study, and he/she considers the event to be reasonably related to the study intervention or study participation, the Investigator must promptly notify the Sponsor.

8.3.2 Method of detecting AEs and SAEs

Care will be taken not to introduce bias when detecting AEs and/or SAEs. Open-ended and nonleading verbal questioning of the participant is the preferred method to inquire about AE occurrences.

8.3.3 Follow-up of AEs and SAEs

After the initial AE/AESI/SAE report, the Investigator is required to proactively follow each participant at subsequent visits/contacts. At the prespecified study end-date, all SAEs and AESI (as defined in [Section 8.3.9](#)), will be followed until resolution, stabilization, the event is otherwise explained, or the participant is lost to follow-up (as defined in [Section 7.4](#)). Further information on follow-up procedures is provided in Appendix 3 ([Section 10.3](#)).

8.3.4 Regulatory reporting requirements for SAEs

- Prompt notification by the Investigator to the Sponsor of an SAE is essential so that legal obligations and ethical responsibilities towards the safety of participants and the safety of a study intervention under clinical investigation are met.
- The Sponsor has a legal responsibility to notify both the local regulatory authority and other regulatory agencies about the safety of a study intervention under clinical investigation. The Sponsor will comply with country-specific regulatory requirements relating to safety reporting to the regulatory authority, Institutional Review Boards (IRB)/Independent Ethics Committees (IEC), and Investigators.
- Serious adverse events that are considered expected will be specified in the IB.
- Investigator safety reports must be prepared for SUSARs according to local regulatory requirements and Sponsor policy and forwarded to Investigators as necessary.
- An Investigator who receives an Investigator safety report describing an SAE, SUSAR, or any other specific safety information (eg, summary or listing of SAEs) from the Sponsor will review and then file it along with the IB and will notify the IRB/IEC, if appropriate according to local requirements. It is the responsibility of the Sponsor to assess whether an event meets the criteria for a SUSAR, and therefore, is expedited to regulatory authorities.

8.3.5 Pregnancy

- Details of all pregnancies in female participants and female partners of male participants will be collected after the start of study intervention and until the time period for post-intervention contraception determined in [Section 5.1](#).
- If a pregnancy is reported, the Investigator will record pregnancy information on the appropriate form and submit it to the Sponsor within 24 hours of learning of the pregnancy of a female participant or female partner of male participant after obtaining the necessary signed informed consent from the female partner.
- Abnormal pregnancy outcomes (eg, spontaneous abortion, fetal death, stillbirth, congenital anomalies, ectopic pregnancy) are considered SAEs and will be reported as such.
- The participant or female partner of male participant will be followed to determine the outcome of the pregnancy. The Investigator will collect follow-up information on the participant or female partner of a male participant and the neonate, and the information will be forwarded to the Sponsor.
- Any poststudy pregnancy-related SAE considered reasonably related to the study intervention by the Investigator will be reported to the Sponsor as described in [Section 8.3.4](#). While the Investigator is not obligated to actively seek this information in former study participants, he/she may learn of an SAE through spontaneous reporting.
- Any female participant who becomes pregnant while participating in the study will discontinue study intervention or be withdrawn from the study.

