4 STUDY DESIGN

4.1 OVERALL DESIGN

Study ACT16753 is a Phase 2, randomized, double-blind placebo-controlled 2 parallel-arm study followed by an open-label, long-term extension period.

The study consists of 2 parts (A and B) as follows:

Part A is a 48-week, double-blind, placebo-controlled part, preceded by a screening period of up to 4 weeks before Day 1.

- The screening period will be up to 4 weeks and is designed to evaluate suitability for participation in the study in terms of MS diagnosis, clinical status based on EDSS, and safety screening evaluations. No IMP will be administered in this period.
- The double-blind treatment period will have a total duration of 48 weeks for each participant and will include the following:
 - Participants will be randomized at 1:1 ratio to receive SAR443820 20 mg QD (n = 84) or matching placebo QD (n = 84).
 - Randomization will be stratified by MS clinical subtypes (ie, RRMS, SPMS, or PPMS) in order to ensure a balance between the treatment and placebo arms within each MS clinical subtype. Participants will attend in-clinic study assessments at baseline (Day 1) and Weeks 2, 4, 6, 8, 9, 10, 12, 14, 16, 18, 20, 22, 24, 28, 32, 40, 44 and 48 (Weeks 4, 8, 9, 10, 14, 16, 18, 20, 22, 28, 32, 40, and 44 visits for liver chemistry only may be conducted at local labs and via home health nursing where available).

All participants who successfully completed Part A will rollover to Part B. Participants who discontinue the treatment or choose not to enter Part B will have their early discontinuation or safety follow-up visit, respectively, up to 2 weeks after the last dose of IMP.

Part B is an open-label, long-term extension of Part A. Part B starts from the end of Part A (Week 48) and continues up to Week 96.

- The assignment of participants to study intervention in Part A will remain double-blinded during Part B unless there is medical need to unblind the study intervention assignment.
- All participants will receive 20 mg QD SAR443820 in Part B.
- Participants will attend in-clinic study assessments at Weeks 50, 52, 54, 56, 58, 60, 62, 64, 66, 68, 70, 72, 76, 80, 84, 88, 92 and 96 (and Week 48 which is the last visit of Part A and first visit of Part B; Weeks 50, 54, 56, 58, 60, 62, 64, 66, 68, 70, 76, 80, 84, 88, and 92 visits for liver chemistry only may be conducted at local labs and via home health nursing where available).

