5.1 INCLUSION CRITERIA

Participants are eligible to be included in the study only if all of the following criteria apply:

Age

I 01. Participant must be 18 to 60 years (inclusive) of age, at the time of signing the informed consent.

Type of participant and disease characteristics

I 01. Participants with a diagnosis of RRMS, SPMS (relapsing or non-relapsing), or primary progressive subtype according to the 2017 revision of the McDonald diagnostic criteria (SPMS diagnostic criteria according to [13] include an initial relapsing remitting disease course followed by progression with or without occasional relapses, minor remissions, and plateaus; progression denotes the continuous worsening of neurological impairment over at least 6 months).

I 02. Participants with an Expanded Disability Status Scale score of 2-6 inclusive at screening.

I 03. Participants who are either untreated or in the opinion of the Investigator are stable on an allowed DMT (interferons, glatiramer acetate, fumarates, or teriflunomide) for at least the past 3 months, AND not anticipated to require a change in MS treatment for the duration of Part A and Part B (through Week 96); in Part B changes in dose of allowed DMTs or transition to other allowed DMTs is permitted).

Weight

I 04. Participants with body weight ≥ 45 kg and body mass index (BMI) ≥ 18.0 kg/m².

Sex, contraceptive/barrier method, and pregnancy testing requirements

I 05. All

Contraceptive use by men and women should be consistent with local regulations regarding the methods of contraception for those participating in clinical studies.

a) Male participants

- Male participants are eligible to participate if they agree to the following during the study period and for at least 92 days following their last dose of IMP:
- Refrain from donating or cryopreserving sperm
Plus, either:
- Be abstinent from heterosexual intercourse as their preferred and usual lifestyle (abstinent on a long-term and persistent basis) and agree to remain abstinent

OR

- Must agree to use contraception/barrier (male condom) as detailed below:
A male condom and an additional highly contraceptive method as described in [Section 10.4.2](#) when having sexual intercourse with a woman of childbearing potential (WOCBP) who is not currently pregnant

b) Female participants

Female participants are eligible to participate if they are not pregnant or breastfeeding and 1 of the following conditions applies:

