- Are a woman of nonchildbearing potential (WONCBP) as defined in [Section 10.4.1](#).

OR

- Are a WOCBP and agree to use a contraceptive method that is highly effective (with a failure rate of <1% per year), preferably with low user dependency, as described in [Section 10.4.2](#) during the study intervention period (to be effective before starting the study intervention) and for at least 32 days after the last administration of the IMP, and agree not to donate or cryopreserve eggs (ova, oocytes) for the purpose of reproduction during this period.
- WOCBP must have a negative highly sensitive pregnancy test within 24 hours before the first administration of the study intervention, see [Section 8.2.6](#).
- If a urine test cannot be confirmed as negative (eg, an ambiguous result), a serum pregnancy test is required. In such cases, the participant must be excluded from participation if the serum pregnancy result is positive.

Informed consent

I 06. Participants are capable of giving signed informed consent as described in Appendix 1 ([Section 10.1](#)) of the protocol which includes compliance with the requirements and restrictions listed in the informed consent form (ICF) and in this protocol.

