- The Investigator will attempt to collect pregnancy information on any male participant's female partner who becomes pregnant while the male participant is in this study. This applies only to male participants who receive the IMP.
- After obtaining the necessary signed informed consent from the pregnant female partner directly, the Investigator will record pregnancy information on the appropriate form and submit it to the Sponsor within 24 hours of learning of the partner's pregnancy. The female partner will also be followed to determine the outcome of the pregnancy. Information on the status of the mother and child will be forwarded to the Sponsor. Generally, the follow-up will be no longer than 6 to 8 weeks following the estimated delivery date. Any termination of the pregnancy will be reported regardless of fetal status (presence or absence of anomalies) or indication for the procedure.

For female participants who could become pregnant:

[figure not shown]
- The Investigator will collect pregnancy information on any female participant who becomes pregnant while participating in this study. The initial information will be recorded on the appropriate form and submitted to the Sponsor within 24 hours of learning of a participant's pregnancy.
- The participant will be followed to determine the outcome of the pregnancy. The Investigator will collect follow-up information on the participant and the neonate and the information will be forwarded to the Sponsor. Generally, follow-up will not be required for longer than 6 to 8 weeks beyond the estimated delivery date. Any termination of pregnancy will be reported, regardless of fetal status (presence or absence of anomalies) or indication for the procedure.
- Any pregnancy complication or elective termination of a pregnancy for medical reasons will be reported as an AE or SAE.
- A spontaneous abortion (occurring at 22 weeks gestational age) is always considered to be an SAE and will be reported as such.
- Any poststudy pregnancy related SAE considered reasonably related to the study intervention by the Investigator will be reported to the Sponsor as described in [Section 8.3.4](#). While the Investigator is not obligated to actively seek this information in former study participants, he or she may learn of an SAE through spontaneous reporting.
- Any female participant who becomes pregnant while participating in the study will discontinue the study intervention or be withdrawn from the study.

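### Protocol 8.3.5 collects pregnancies through the 32-day (women) and 92-day (men) post-dose contraception periods, but 10.4.2 collects them only during study participation, and no planned contact reaches the end of either period for those who complete or leave

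*Protocol*

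**What the plan says.** **The longer window.** Protocol Section 8.3.5 covers women in the trial and the partners of men in the trial. It says that information on every pregnancy among them "will be collected after the start of study intervention and until the time period for post-intervention contraception determined in" the inclusion criteria (Section 5.1). Inclusion criterion I 05 in Section 5.1 sets that period for men "for at least 92 days following their last dose of IMP" and for women of childbearing potential "for at least 32 days after the last administration of the IMP".

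**The shorter window.** Section 10.4.2, under collection of pregnancy information, asks the investigator to attempt to collect information on "any male participant's female partner who becomes pregnant while the male participant is in this study", and to collect it on "any female participant who becomes pregnant while participating in this study". The same section repeats the 32-day and 92-day contraception periods.

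**The schedule.** Section 4.1 places the early discontinuation or safety follow-up visit, for those who stop treatment or do not enter Part B, "up to 2 weeks after the last dose of IMP". Footnote b of the Part B schedule gives a safety follow-up visit, also within 2 weeks, to people who do not wish to stay in the study. Footnote i lists Week 96 as the last clinic visit with a pregnancy test. The synopsis gives a total duration of about 100 weeks.

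**Status of the event.** Section 8.3.9 makes pregnancy, including partner pregnancy, an AESI to be notified within 24 hours, with mandatory follow-up to outcome. For AEs and SAEs in general, Section 8.3.1 says "Investigators are not obligated to actively seek information on AEs or SAEs after conclusion of the study participation".

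**The concern.** Two current sections give different end points for collecting the same safety event, and the visit schedule serves only the earlier one. The protocol asks for contraception for 32 or 92 days after the last dose and, in 8.3.5, ties pregnancy collection to those same days. A site that works from 10.4.2 and the schedule has no planned occasion on which to learn of a conception in most of that time.

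Two things are at stake: the completeness of post-treatment pregnancy reporting, and the mandatory outcome follow-up in 8.3.9, which cannot begin for a pregnancy the site never hears about. Partner pregnancies are the most exposed because their window is the longer. Sites could also differ simply because they follow different sections. No efficacy endpoint is involved.

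**Working it through.** **Inputs**
- Length of the post-dose window, W: at least 32 days for women and at least 92 days for men (Section 5.1, I 05).
- Last planned contact after last dose, c: between 0 days (Week 96/EOT is the final visit) and 14 days (Section 4.1; Part B schedule, footnote b; Section 7.2).
- Total duration: about 100 weeks (synopsis).

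**Step 1: reproduce the stated duration.** Screening 4 + Part A 48 + Part B 48 = 100 weeks. This matches the synopsis without any post-treatment period, although the figure is approximate and could absorb a 2-week visit.

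**Step 2: share of the window with no planned contact,** (W − c)/W.

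| Group | W (days) | c (days) | Uncovered days | Share |
|---|---|---|---|---|
| Women | 32 | 14 | 32 − 14 = 18 | 18/32 = 56% |
| Men (partners) | 92 | 14 | 92 − 14 = 78 | 78/92 = 85% |
| Women | 32 | 0 | 32 | 100% |
| Men (partners) | 92 | 0 | 92 | 100% |

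The c = 14 rows are the most favourable case for someone who completes or leaves the study. Because both contraception periods are stated as minimums, 56% and 85% are lower bounds.

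**Step 3: who is not affected.** Section 7.1.1 follows participants who permanently stop IMP to study completion, and Section 7.2 encourages them to remain. Their window is spanned by scheduled visits if the last dose is at least 32/7 = 4.6 weeks (women) or 92/7 = 13.1 weeks (men) before their last visit. With a last visit at Week 96, that means stopping by about Week 91 (96 − 4.6 = 91.4) or Week 82 (96 − 13.1 = 82.9).

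**Step 4: effect on the planned tables.** SAP Section 3.1 closes the treatment-emergent period no later than last IMP + 14 days, and SAP Section 3.6.2 tabulates treatment-emergent AESIs. A pregnancy arising on days 15 to 92 falls outside that table whichever protocol section a site follows. Only the post-treatment summaries and listings can change.

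**The case against.** **The two sections can both be obeyed.** Section 10.4.2 states a duty for pregnancies arising during the study and does not forbid later collection. Section 8.3.9 covers anyone entered in the trial without an on-study limit. A careful site could therefore follow 8.3.5 and breach nothing. This stands as far as it goes, but the schedule gives that site no contact at which to do it, and a site that reads only 10.4.2 would stop earlier.

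**Absence of a visit is not absence of reporting.** Participants may report spontaneously, and a reported pregnancy must reach the sponsor within 24 hours. Consent pages are not available, so instructions to participants cannot be judged missing. This also stands. However, Section 8.3.5 commits to collecting all pregnancies in the window, and passive reporting does not secure that.

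**Stronger readings that the documents do not support**
- A reader might infer that contact ends within 2 weeks for everyone. It does not for people who stop IMP and stay in the study (Sections 7.1.1 and 7.2; SAP Sections 3.2.4 and 3.3.2 plan to use their later data).
- A reader might infer that completers are wholly uncovered. Footnote b points that way, but Sections 6.8 and 8.3.1 mention a follow-up visit without restricting who attends, and the schedule table is broken in the available text.
- A reader might take 8.3.1 as removing any duty to ask about pregnancy. It is a general AE/SAE clause. The similar sentence in 8.3.5 concerns poststudy pregnancy-related SAEs, not finding pregnancies within the window.
- A reader might expect the main AESI counts to be distorted. The 14-day limit of the treatment-emergent period rules that out for pregnancies arising later.

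**Conclusion.** The inconsistency is in current text and does not depend on redacted material. For participants who complete or leave the study, at least 56% of the women's window and at least 85% of the men's window have no planned contact. The upper bound is 100%, which applies only if completers have no visit after Week 96/EOT.

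This rests on two assumptions: that the 8.3.5 window runs to the end of the contraception period, and that no later contact is specified outside the two documents. If 8.3.5 was meant to stop when that period begins, its wording needs clarifying anyway. The number of pregnancies affected cannot be estimated from the documents. The consequence is limited to incomplete, possibly site-dependent, post-treatment pregnancy reporting and outcome follow-up. It is worth correcting because the event is an AESI and the correction is cheap.

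**What to change.** 1. In Protocol Section 10.4.2, replace the two limits to time in the study (female participants and partners of male participants) with the window in Section 8.3.5, stated explicitly as running to the end of the post-intervention contraception period in Section 5.1.
2. Add to the schedule of activities one remote contact at or shortly after the end of that window, to ask about pregnancy. It applies to women of childbearing potential and to male participants who are not otherwise still in scheduled follow-up. Placing it shortly after the end helps to catch conceptions late in the window that would not yet be recognised on its last day.
3. State in the schedule whether Part B completers attend the safety follow-up visit.

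If the sponsor intends the shorter window, Section 8.3.5 has to be amended and the choice justified; the two texts should not both stand. The contraception periods themselves are not in question here.

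Cost: wording changes and one call per affected participant, with no added visit or sample.
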